4.5. EGG registration

Instruments: The 3CPM electrogastrography device will be used to record GMA before and after the WLST to record GMA. 3CPM EGG SAS GMAT Threshold software will be used for signal analysis. The data will be collected prospectively in a virtual log for blind analysis. (Figure 1)

Figure 1

On the morning of the EGG and water load satiety test, the subject will arrive fasting after midnight. Participants may take their usual medications (e.g antihypertensive medications) with a small amount of water (up to 4 oz) up to two hours prior to the study, but should refrain from coffee, tea, or juice.

At home, the skin of the abdomen should be shaved before for better placement of the electrodes. The typical recording process usually takes a total of 1 hour: A 15 minutes baseline recording, 5 minutes of ingestion of water until “completely full, and a 30 min post-ingestion recording.

Electrogastrographic signals are recorded from electrodes placed in the midline midway between the xiphoid appendage and the umbilicus. The other electrodes are placed in the left and right upper quadrant, respectively, from a straight line from the midpoint of the clavicle and a point 2-3 cm below the left and right -costal border. The belt to record respiration rate is placed above nipples of the chest level and is firmly fixed.

Patients should be seated in a comfortable chair, reclining at about 30-45 degrees and will remain motion-free throughout the test (Fig.2.3).

[figure not shown]

Figure 2

[figure not shown]

Figure 3

A 15 min baseline EGG recording is obtained and then the WLST is given.

Water at from a tap is placed into a 1-liter container from which the patient will drink as directed below. The patient must be given the following instruction about the WLST in precisely the words below:

Diabetic participants' blood glucose level should be checked to ensure it is less than 270 mg/dL. If the participant's blood glucose level is greater than 270 mg/dL, it is either treated and rechecked before proceeding or the EGG and water load satiety test will be rescheduled for another day under better glucose control.

[figure not shown]
Baseline symptoms prior to EGG recording are obtained using 100 mm visual analog scales (VAS) for stomach fullness, hunger, nausea, bloating, and abdominal discomfort. The patient marks each symptom line with a vertical line to indicate how they currently feel in terms of that symptom. Once the EGG and respiratory signals are stable, the baseline EGG recording period can begin.

After the 15 min baseline EGG recording is completed the participants will begin the Water Load Satiety Test. For this, participants will sit upright. During the test, participants

will drink cool water from the 1 liter container (Figure 4). They will drink for a 5-minute period only and until they feel "completely full."

Figure 4

A continuous 30 minute EGG recording is then obtained after the water is consumed. The participant's symptoms are recorded using VAS at 10, 20, and 30 minutes after ingestion of the water (at the end of the 0-10 minute, 11-20 minute, and the 21-30 minute periods after the water load ingestion) (Figure 5). The test is completed after the 30-minute recording period and the electrodes are removed).

Figure 5.- Water Load Stress Test and Visual Analogue Scale

It is important that the research associate at each site gives each subject the very same instructions as follows:

"I want you to drink water from this container until you feel completely full. You have up to five minutes to reach the feeling of completely full. You may stop at any time, up to the five-minute time limit, when you feel completely full. This is not a test to see how much you can drink, but to drink until you are completely full in the five minute period. Do you have any questions about this?"

****The total volume of water consumed will be recorded.***

4.7. EGG signal analysis

EGG signal is reviewed for movement artifacts. Artifact – free minutes are chosen for blinded computer analysis (at baseline, three, six and 12 months recordings and for each type of BE procedure). The selected minutes of EGG are analyzed by spectral analysis

by computer applications. 3CPM EGGSAS GMAT Threshold software will be used for signal analysis. EGG data will be organized by clinical diagnosis. Water load volumes ingested that are <238 ml are considered abnormally low (33).

5.- STATISTIC

The normal distribution of the variables will be confirmed by the kolmogorov-Smirnoff test. Quantitative variables shall be expressed as mean s/e d or means (interquartile range). Comparison between groups will be performed by parametric or nonparametric tests, depending on the distribution of the variables. Spearman or Pearson correlation will be used for the study of correlations. The possibility of multivariate logistic regression analysis will be explored. An SPSS statistical programme will be used. EGG data will be descriptive in terms of overall clinical EGG diagnosis and normal or abnormal water load volume ingested. Symptom data before and after the WLST will be tabulated. These measures will be calculated before and 3 and 6 months after the BE procedures.

6.- STUDY LIMITATIONS

Recruitment of the number of subjects should not be a problem due to the high number of patients performed in the different centers and will allow the selection of those with the most approximate clinical results between groups.

A strength of the study is to have a control group of non-obese subjects, which will allow us to know the normal pattern of GMA in response to the WLST and whether it is similar to those worldwide reported in healthy individuals.

All tests will be carried out by the same expert operator in the medical center and analyzed by one specialist in EGG that received the blinded information from all the centers because it is a multicenter study, but the bariatric procedures will be performed by different operators from every center.

7.- STAGES OF DEVELOPMENT AND DISTRIBUTION OF THE AREAS OF ALL RESEARCH EQUIPMENT

The clinical study will be conducted simultaneously in AIG hospitals, Hyderabad, India, and Gastrodex, Dexeus University Hospital center in Spain. The task layout of the study team members will be as follows:

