Variable weight loss and intolerance of BE procedures are appreciated. For this protocol we define Failure of BE methods when patient only obtain less than 25% of EWL after 6 months of BE, according to the Part 1 of the BAROS (Bariatric Analysis and Reporting Outcome System) scale adapted to endoscopic treatment (2) (Table 1).

After BIG placement, patients present intolerance such vomit and abdominal pain in 70-90% of cases at the first week but these effects can be extended up to three weeks (18%) and removal of the balloon in 4% of patients (3). Gastric emptying measured by gastric scintigraphy breath test or stable isotope breath tests show that there are physiological predictors of intolerance and response to BIG placement (10). Many studies show that patients after ESG at 6 months achieved a mean of 50% of EWL or more with rate of severe adverse events around 2% , including pain or nausea requiring hospitalization, upper gastrointestinal bleeding and peri-gastric leak or fluid collection (11).

After SEG.....

.....

Table 1 . BAROS (BARIATRIC ANALYSIS AND REPORTING OUTCOME SYSTEM) ADAPTED TO BARIATRIC ENDOSCOPY

1. Percentage of excess weight loss (%EWL): (Initial weight – Current weight) / (Initial weight – Ideal weight) × 100 (-1): Weight gain (0): Weight loss 0-24% (+1): Weight loss 25-49% (+2): Weight loss 50-74% (+3): Weight loss > 75%
 
2. Comorbidity: (-1): Aggravated (0): Unchanged (+1): Improved (unresolved) (+2): Improved: one major resolved, others improved (+3): Improved: all majors resolved, others improved
 
3. Quality of life questionnaire: (much worse, worse, unchanged, better, much better) Self-esteem (scale -1, -0.5, 0, +0.5, +1) Physical (scale -0.5, -0.25, 0, +0.25, +0.5) Social (scale -0.5, -0.25, 0, +0.25, +0.5) Work (scale -0.5, -0.25, 0, +0.25, +0.5) Sex (scale -0.5, -0.25, 0, +0.25, +0.5)
 
4. Complications: (-0.2): Per minor complication (-1): Per major complication (-1): In case of repeat endoscopy or surgery
	
Final score (sum total of above 4 items)
 
• No comorbidities: Failure: 0 or less Fair: 0-1.5 Good: 1.5-3 Very good: 3-4.5 Excellent: 4.5-6• Comorbidities: Failure: < 1 Fair: 1-3 Good: 3-5 Very good: 5-7 Excellent: 7-9
--	--

Thus, a fuller understanding of gastric physiology before undertaking BE treatments may lead to better patient selection for each procedure.

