Demonstrate the usefulness of EGG measuring the GMA by identifying subtypes with the Water Load Satiety Test (WLST) in obese adults to predict individual successful responses to BE treatments: Intra-gastric Balloon (IGB) placement and Apollo Endoscopic Sleeve Gastroplasty (ESG) method.

Demonstrate the usefulness of EGG measuring the GMA by identifying subtypes with the Water Load Satiety Test (WLST) in obese adults to predict individual successful responses to BE treatments: Intra-gastric Balloon (IGB) placement and Apollo Endoscopic Sleeve Gastroplasty (ESG) method

3.- OBJECTIVES

3.1.- Primary Objective –

- . Pre-intervention EGG parameters and/or changes in EGG parameters (one/three months) after bariatric intervention can predict clinical success at the end of follow up
- a. Pre-intervention EGG parameters and/or changes in EGG parameters after the bariatric intervention can predict adverse events at the end of follow-up.

3.2. Secondary:

- a. Secondary Objective
To predict suitable bariatric intervention for patients depending upon a pre-intervention EGG.
- b. EGG is a feasible diagnostic tool in obese population with reproducible and predictable results

4.- STUDY DESIGN AND METHODOLOGY

4.1. Type of study: Multicenter, prospective, observational study in patients with body mass index (BMI) at 30 kg/m² prior and after one, and three, six and 12 months of a bariatric procedure. All tests will be analyzed by one blinded specialist.

4.2. Study design: This is a pilot study, involving 2 hospitals in Spain and India, where 4 groups of patients will be recruited.

- a) Group of 50 patients who will undergo BIG placement
- b) Group of 50 patients who will undergo Endoscopic Sleeve Gastroplasty (ESG) Apollo method.
- c) Group of 50 patients who will undergo Surgical Sleeve Gastrectomy (SEG) Apollo method

d) Group of 50 patients who will undergo RYGB method

The protocol will be carried out in the run-up to the BE procedure until 12 months after of follow up. As a control group, 50 people (of the same age and gender) will be selected, with BMI less than 25% who voluntarily agree to participate in the protocol and have the same criteria of inclusion or exclusion of patients that belongs to all the groups, except BMI.

Duration – 18 months to 24 months

4.3. Characteristics of subjects:

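### Secondary objective (a) asks which procedure suits which pre-intervention EGG, but the analyses named in Section 5 do not compare the EGG-outcome relation between procedures, and the outcome time point is not settled

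*Protocol*

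**What the plan says.** Section 3.2 states secondary objective (a): "To predict suitable bariatric intervention for patients depending upon a pre-intervention EGG". The Summary announces the same use, with EGG subgroups guiding which patients receive which procedure. Section 4.2 plans four non-randomised groups of 50 (balloon, ESG, surgical sleeve, RYGB) and calls the study a pilot.

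Section 5 lists the analyses. Groups are compared as follows: "Comparison between groups will be performed by parametric or nonparametric tests, depending on the distribution of the variables". It continues: "Spearman or Pearson correlation will be used for the study of correlations. The possibility of multivariate logistic regression analysis will be explored". On EGG it adds: "EGG data will be descriptive in terms of overall clinical EGG diagnosis and normal or abnormal water load volume ingested". No outcome, predictor or EGG-by-procedure term is named for the logistic model.

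On timing, Section 5 says "These measures will be calculated before and 3 and 6 months after the BE procedures". The primary objective (Section 3.1) is that EGG parameters "can predict clinical success at the end of follow up", and Section 4.2 says "The protocol will be carried out in the run-up to the BE procedure until 12 months after of follow up". Section 1.3 sets failure at another time and for endoscopic procedures only: "we define Failure of BE methods when patient only obtain less than 25% of EWL after 6 months of BE".

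**The concern.** To recommend a procedure because of a patient's EGG, one must show that the effect of EGG on outcome depends on the procedure. The tools named in Section 5 give related but different answers:

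- A whole-group test compares procedures and ignores EGG.
- A correlation pooled over procedures averages the EGG effect and mixes it with differences between procedures.
- A correlation within each procedure gives separate associations, but not the difference between them.
- A comparison of procedures within one EGG class bears on (a). It also picks up any general advantage of one procedure, so on its own it cannot show that EGG changes the choice.
- A logistic model without an EGG-by-procedure term has the same gap.

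At stake is a claim that one procedure is best for a given EGG pattern, when the pattern plays no part. The unsettled time point adds to this, because any analysis of (a) could be run at 6 or at 12 months and the protocol does not say which governs.

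**Working it through.** The protocol gives no alpha, power or effect size for (a), so there is no planned figure to reproduce. From the documents come 50 per group (Section 4.2) and a mean excess weight loss (EWL) after ESG of 50% or more at 6 months (Section 1.3). Assumed are two-sided 5%, a comparator mean of 35%, an SD of 20 or 25 points, and 10 or 25 abnormal EGGs per 50.

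**1. Separate verdicts by EGG class, no EGG effect.** Two procedures differ by 15 points in both classes. A t-test between procedures within a class with n per procedure has standard error SD × √(2/n). If the tests have power p0 (normal EGG) and p1 (abnormal EGG), they disagree with probability p0(1−p1) + p1(1−p0).

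| SD | Abnormal per 50 | p0 | p1 | Verdicts differ |
|---|---|---|---|---|
| 20 | 10 | 0.912 | 0.355 | 0.619 |
| 20 | 25 | 0.738 | 0.738 | 0.386 |
| 25 | 10 | 0.755 | 0.246 | 0.630 |
| 25 | 25 | 0.547 | 0.547 | 0.496 |

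The range is about 39-63%. In simulation the interaction test was positive in about 5% in the same settings.

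**2. Separate correlations per procedure.** With n = 50 the Fisher z standard error is 1/√47. If the true r is 0.3 in every procedure, each test has power 0.564. Two procedures then disagree in 2 × 0.564 × 0.436 = 49% of studies. Four are not unanimous in 1 − 0.564⁴ − 0.436⁴ = 86%.

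**3. A real crossover.** Suppose abnormal EGG adds 15 points with one procedure and subtracts 15 with the other.

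- The pooled EGG effect averages to zero. The pooled test was positive in 1-4% of simulated studies (base means 50/50 and 35/50).
- The interaction test was positive in 66-96%.
- Comparing procedures within abnormal EGG, with equal base means, the gap is 30 points and the t-test has power 0.718-0.999.
- With base means 35 and 50 the within-class result depends on direction. Power is 97% or more when the crossover widens the gap, and 25-74% when it reverses it.

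**4. Precision of the interaction.** For a abnormal and b normal EGGs per procedure, the standard error of the difference in EGG effect between two procedures is SD × √(2(1/a + 1/b)).

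- SD 20, 25/25: 20 × √0.16 = 8.0. Detectable with 80% power: 2.80 × 8.0 = 22.4 points.
- SD 25, 10/40: 25 × √0.25 = 12.5. Detectable: 2.80 × 12.5 = 35.0 points.

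**5. Time points side by side.**

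| Place | Time |
|---|---|
| Section 3.1, success | end of follow-up |
| Section 4.2, follow-up | 12 months |
| Section 4.7, EGG recordings | baseline, 3, 6 and 12 months |
| Section 5, measures | before, 3 and 6 months |
| Section 1.3, failure (endoscopic only) | 6 months |
| Closing timetable | baseline, 3 and 6 months |

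**The case against.** The strongest reply is that covariates and model form usually belong in the SAP, which may exist. Section 5 leaves regression open and does not rule out an interaction term. That is fair. One might infer that the plan forbids the right analysis, but the text does not go that far. What remains is that the analyses it does name are not matched to a stated objective.

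Three other strong readings are tempting and are not supported:

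- **All EGG data are descriptive only.** The sentence covers the overall EGG diagnosis and the water-load volume. Section 4.4 also collects percentage distributions and ratios, which may be correlated with outcome.
- **The within-class significance rates are false positives.** They are power for a procedure difference that was assumed to be true. If one procedure is better in both classes, it is better for that EGG pattern too. The error arises only if differing verdicts are read as evidence that EGG changes the choice.
- **The named tools would generally miss a crossover.** That holds mainly for pooling, which the protocol does not say it will do. A within-class comparison often detects it (item 3).

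On timing, the 3- and 6-month sentence directly follows the EGG and symptom sentences, so it may not set the time of the weight outcome. That is possible, but no other sentence in Section 5 sets it.

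Finally, (a) is secondary in a non-randomised pilot, and the interaction test is itself weak: for a 15-point difference its power is only about 22-46%. This is a reason to report an estimate with its interval and to label (a) exploratory. It does not justify relying on separate p-values.

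**Conclusion.** The point holds in limited form. Objective (a) is an EGG-by-procedure question, and the tools named in Section 5 do not, as described, compare the EGG-outcome relation between procedures. If separate p-values were used to answer it, differing verdicts would arise in about 39-63% of studies with no EGG effect, against about 5% for the interaction test. These figures depend on the assumed means, SDs and EGG shares, and on (a) being answered that way, which the protocol neither says nor excludes. The time-point mismatch is a plain inconsistency in the text and needs no assumption. Because procedures are not randomised and, per Section 6, operators differ between centres, any answer to (a) stays observational. The change is worth making, but it does not put the primary objective in doubt.

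**What to change.** In Section 5, for objective (a):

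- Commit to one exploratory linear model of % excess weight loss with procedure, pre-intervention EGG (normal/abnormal diagnosis or one named measure), EGG × procedure, baseline BMI, and centre where it can be estimated. A continuous outcome suits all four groups, because Section 1.3 defines failure for endoscopic procedures only.
- Report the interaction, and the EGG effect in each procedure, with 95% confidence intervals. State that separate p-values by procedure or EGG class will not be compared.
- Name one time point. Either add 12 months to Section 5 and align the closing timetable, or reword the success criterion in Section 3.1 to 6 months.
- Label (a) in Section 3.2 as exploratory and hypothesis-generating.

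The cost is wording plus one model, with no added patients or visits beyond the 12-month follow-up already planned. The drawback is low precision: under the assumed SDs and EGG shares, differences in EGG effect below about 22-35 points will mostly stay unresolved, and the text should say so.

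### The primary objective is prediction of success and adverse events, but Section 5 commits only to summaries, group tests and correlations and leaves the one patient-level model optional

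*Protocol*

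**What the plan says.** **Objectives.** The aim stated just before Section 3 is to use EGG with the water load test "to predict individual successful responses to BE treatments". Section 3.1 makes two predictive claims primary. Pre-intervention EGG parameters, or their changes at one or three months, "after bariatric intervention can predict clinical success at the end of follow up", and EGG parameters or their changes "can predict adverse events at the end of follow-up". The first secondary objective in Section 3.2 is also predictive: "To predict suitable bariatric intervention for patients depending upon a pre-intervention EGG".

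**Analysis.** Besides a normality check and summary statistics, Section 5 commits to two inferential methods: "Comparison between groups will be performed by parametric or nonparametric tests, depending on the distribution of the variables" and "Spearman or Pearson correlation will be used for the study of correlations". It does not say which groups are compared or which variables are correlated. Regression appears once: "The possibility of multivariate logistic regression analysis will be explored". Its outcome and predictors are not named. On the EGG itself: "EGG data will be descriptive in terms of overall clinical EGG diagnosis and normal or abnormal water load volume ingested". Discrimination, sensitivity, specificity, predictive value and validation are not mentioned in the text shown.

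**Outcome and timing.** Section 1.3 defines failure of the endoscopic methods as less than 25% excess weight loss at 6 months. Section 5 does not refer to that definition. Section 4.2 runs follow-up to 12 months, while Section 5 calculates its measures before the procedure and at 3 and 6 months.

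**The concern.** A test of means or a correlation asks whether EGG and outcome are associated on average. The primary objective asks something harder: whether EGG tells a clinician which patient will succeed. An association can be statistically convincing while the distributions of responders and non-responders overlap almost completely.

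The four procedures differ, and patients are not randomised between them. A pooled, unadjusted association could therefore reflect procedure or baseline BMI and not EGG. Only a model containing those variables, with and without EGG, shows whether EGG adds anything.

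The protocol wants the result to guide patient selection. If Section 5 is followed exactly as written and the regression is not pursued, the study can end without an estimate that answers its primary question.

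**Working it through.** The protocol has no figure to reproduce: it states no alpha, power, effect size or failure rate. The calculation below only illustrates how far significance and prediction can diverge.

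**Inputs from the protocol (Section 4.2).** Four procedure groups of 50, so 4 × 50 = 200 treated patients.

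**Assumptions.** Two-sided alpha 0.05; a normally distributed EGG marker with equal SD in responders (n0) and non-responders (n1); failure share 10% to 50%.

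**Formulas.**
- Smallest standardised difference reaching p = 0.05: d = t(0.975, n − 2) × √(1/n1 + 1/n0).
- AUC = Φ(d/√2).
- Sensitivity = specificity at the midpoint cut = Φ(d/2).

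**Worked cases at 20% failures.**
- Pooled, 40 v 160: d = 1.972 × √(1/40 + 1/160) = 1.972 × 0.177 = 0.35. AUC = Φ(0.247) = 0.60. Sensitivity = specificity = Φ(0.174) = 57%.
- One group, 10 v 40: d = 2.011 × √(1/10 + 1/40) = 2.011 × 0.354 = 0.71. AUC = Φ(0.503) = 0.69. Sensitivity = specificity = Φ(0.355) = 64%.

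**Range over the assumed failure share.**

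| Failures | n = 200: d | n = 200: AUC | n = 50: d | n = 50: AUC |
|---|---|---|---|---|
| 10% | 0.46 | 0.63 | 0.95 | 0.75 |
| 20% | 0.35 | 0.60 | 0.71 | 0.69 |
| 30% | 0.30 | 0.59 | 0.62 | 0.67 |
| 50% | 0.28 | 0.58 | 0.57 | 0.66 |

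**Correlation.** The smallest significant |r| is t/√(n − 2 + t²). For n = 200 this is 0.14, or 2% of variance. For n = 50 it is 0.28, or 8%.

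**Precision if the AUC were reported.** The Hanley-McNeil variance is [A(1 − A) + (n1 − 1)(Q1 − A²) + (n0 − 1)(Q2 − A²)]/(n1·n0), with Q1 = A/(2 − A) and Q2 = 2A²/(1 + A). For A = 0.75, Q1 = 0.600 and Q2 = 0.643. At 20% failures:
- Pooled (40 v 160): SE 0.0475, 95% half-width 1.96 × 0.0475 = 0.09.
- One group (10 v 40): SE 0.0956, 95% half-width 0.19.

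**Room for a model.** With 40 failures, adjusting for procedure (3 parameters), BMI, age, sex and centre takes 7 parameters before EGG enters. Five EGG categories would add 4, giving 40/11 = 3.6 failures per parameter. Procedure, BMI and one binary EGG variable take 3 + 1 + 1 = 5 parameters, giving 40/5 = 8. At 10% failures, that smaller model has only 20/5 = 4.

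**The case against.** **An SAP may supply the detail.** Model terms, accuracy measures and validation are commonly left to an SAP, and logistic regression is a suitable family that the protocol does name. That stands for the detail. It does not cover the status of the method: the protocol makes tests and correlations firm and the patient-level model optional, against its own primary objective.

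**It is a pilot.** Section 4.2 says so, and a pilot may reasonably be descriptive. In that case the objective should not be worded as a predictive claim. One of the two needs editing.

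**Stronger readings that the text does not support.**
- A reader might infer that the EGG is excluded from inference, because Section 5 calls EGG data descriptive. That sentence can equally be naming the categories used to summarise EGG; it does not bar EGG from the tests or the regression.
- A reader might infer that the planned tests cannot yield any accuracy measure. If the groups were responders and non-responders, the Mann-Whitney statistic divided by n1·n0 is the AUC. Section 5 neither defines the groups that way nor names the AUC, so the fair statement is that no accuracy measure is named.
- A reader might infer that a significant test will be reported as successful prediction. The protocol sets no rule for concluding that EGG predicts, so it could happen, and no more can be said.

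**The pooled 200 may be too many.** The aim before Section 3 names only the balloon and endoscopic sleeve groups, 100 patients. Section 3.1 refers to bariatric intervention generally, so pooling is defensible. With 100 patients (20 v 80), d = 1.984 × 0.25 = 0.50 and the AUC is 0.64, between the two cases shown.

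**Conclusion.** The concern holds as a mismatch between objective and committed analysis. The primary objective is prediction; the firm methods measure association; the patient-level model is optional and no accuracy measure is named.

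Under the stated assumptions, a just-significant pooled result implies an AUC between 0.58 and 0.63, and one within a single procedure group an AUC between 0.66 and 0.75. The pooled figures in particular are weak grounds for selecting patients. They depend on an assumed alpha, failure share and normal continuous marker, and do not directly describe a categorical EGG diagnosis. The mismatch itself depends on none of these assumptions.

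The data would remain usable, so this should be corrected but does not invalidate the study.

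**What to change.** In Section 5, replace the sentence on exploring regression with a committed primary analysis:

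1. **Outcome.** Fix one definition of success and one time point. Reconcile the 6-month failure definition in Section 1.3, which is worded for endoscopic methods only, with the 12-month end of follow-up in Section 4.2 and with the surgical groups.
2. **Model.** Fit a small prespecified or penalised logistic model with procedure and baseline BMI, with and without one prespecified pre-intervention EGG variable (for example normal v abnormal diagnosis).
3. **Reporting.** Give the AUC and its gain from adding EGG with 95% confidence intervals, and sensitivity and specificity, bootstrap-corrected for optimism.
4. **Rest of the primary objective.** Treat adverse events and the one- and three-month EGG changes in the same way where event numbers allow.
5. **Existing methods.** Keep group tests and correlations as descriptive support.

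If the team does not want to commit to this, reword the primary objective as exploratory association, which fits the pilot label.

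The cost is more analysis work; no added patients or visits are needed. The drawback is wide intervals (95% half-width at an AUC of 0.75 about 0.09 pooled and 0.19 in one group, at 20% failures), which should be shown. If failures are few, even the small model will need penalisation.

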Voluntary patients with obesity will be recruited among those patients who will be given any of the four types of bariatric procedures described above, at the time before and after the first, third, sixth and 12 months of performing the bariatric methods.

Patients will be recruited in AIG Hospitals, Gachibowli, Hyderabad

Inclusion criteria:

1. Men and women, aged between 18-65 yrs
2. IMC basal ≥ 30 kg/m²
3. Patient undergoing bariatric intervention willing to participate in the study
4. Informed consent (oral and written) for the tests to be carried out.

Exclusion criteria:

1. Presence of severe cardiac, renal, hepatic, or neurological disease
2. Long term use of medication that alter gastric motility (> 4 weeks)
3. Significant alcohol or opioids or narcotics or tobacco
4. Active malignancy
5. Pregnancy
6. Uncontrolled Diabetes Mellitus with glycosylated hemoglobin (HbA1c) levels $\geq 6.5\%$ or glucose level more than 270 mg/dL.
7. Uncontrolled hypothyroidism (High TSH with low levels of Free T4)

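### The primary question has no single set of time points: the 1-month EGG change is left out of both analysis lists, and clinical success can be read at 6 or at 12 months

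*Protocol*

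**What the plan says.** The primary objective (Section 3.1) reads: "Pre-intervention EGG parameters and/or changes in EGG parameters (one/three months) after bariatric intervention can predict clinical success at the end of follow up".

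The assessment times are given in several places:

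- Section 4.1: "prior and after one, and three, six and 12 months of a bariatric procedure".
- Section 4.3: "at the time before and after the first, third, sixth and 12 months of performing the bariatric methods".
- Section 4.2, on the length of follow-up: "The protocol will be carried out in the run-up to the BE procedure until 12 months after of follow up". It gives the study duration as "18 months to 24 months".
- Section 4.7, on the recordings from which EGG minutes are chosen for blinded analysis: "at baseline, three, six and 12 months recordings and for each type of BE procedure".
- Section 5, after listing EGG diagnosis, water volume and symptoms: "These measures will be calculated before and 3 and 6 months after the BE procedures".
- The timeline paragraph before the bibliography: baseline, three and six months, with execution taking about 18 months.

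The only numerical outcome rule adopted for this protocol is in Section 1.3: "we define Failure of BE methods when patient only obtain less than 25% of EWL after 6 months of BE".

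**The concern.** A prediction study needs two times fixed in advance: when the predictor is measured and when the outcome is judged. Here neither is settled.

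On the predictor side, the 1-month EGG change is named in the primary objective and has a scheduled visit. The two sections that say which recordings are analysed both leave it out. Anyone following Sections 4.7 and 5 as written would collect the recording and not use it.

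On the outcome side, Sections 3.1 and 4.2 together point to 12 months, while the only rule that separates failure from success is set at 6 months. The same patient can fail at one time and not at the other. If neither is chosen beforehand, the time that shows the stronger association with EGG can be picked afterwards. The failure rule is also worded for endoscopic methods. The surgical groups have only the end of follow-up to go by, so nothing in the text prevents endoscopic patients being classified at 6 months and surgical patients at 12 within one analysis. Outcome timing would then be mixed up with type of procedure, which bears directly on the secondary objective of choosing a procedure from the baseline EGG.

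**Working it through.** **Time points side by side (months; 0 = baseline)**

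| Place in protocol | 0 | 1 | 3 | 6 | 12 |
|---|---|---|---|---|---|
| 3.1, EGG predictors | yes | yes | yes | – | – |
| 4.1 and 4.3, visits | yes | yes | yes | yes | yes |
| 4.7, EGG recordings analysed | yes | – | yes | yes | yes |
| 5, measures calculated | yes | – | yes | yes | – |
| Timeline paragraph | yes | – | yes | yes | – |

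Outcome time: end of follow-up in 3.1, which is 12 months by 4.2; 6 months in the failure rule of 1.3.

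There are three distinct visit sets: {0, 1, 3, 6, 12}, {0, 3, 6, 12} and {0, 3, 6}. Only {0, 3, 6} is common to all of them. The 1-month EGG is in none of the analysis lists. The 12-month recordings selected in 4.7 are dropped in 5.

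**Coverage of the failure rule.** Section 4.2 plans four procedure groups of 50, so 4 × 50 = 200. The rule as worded fits balloon and endoscopic sleeve: 50 + 50 = 100 of 200.

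**How many patients could change class.** This is an illustration for the endoscopic sleeve group (n = 50).

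- From Section 1.3: the cut is 25% excess weight loss, and the mean at 6 months is 50% or more.
- Assumed, not in the protocol: the mean is exactly 50% at both times, the SD is 20 to 30 points at both, the 6-to-12-month correlation ρ is 0.7 to 0.9, and the two values are bivariate normal.

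With z = (25 − 50)/SD, P(fail at each time) = Φ(z), and P(class differs) = 2 × [Φ(z) − Φ₂(z, z; ρ)], where Φ₂ is the bivariate normal probability of failing at both times.

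| SD | z | P(fail) | Class differs, ρ = 0.7 | ρ = 0.8 | ρ = 0.9 |
|---|---|---|---|---|---|
| 20 | −1.25 | 10.6% | 11.1% | 9.1% | 6.5% |
| 25 | −1.00 | 15.9% | 14.9% | 12.2% | 8.6% |
| 30 | −0.83 | 20.2% | 17.5% | 14.3% | 10.1% |

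Of 50 patients, about 5 to 10 fail at each time (50 × 0.106 = 5.3; 50 × 0.202 = 10.1). About 3 to 9 change class (50 × 0.065 = 3.2; 50 × 0.175 = 8.8). Under the same assumptions, the share of 6-month failures that are not failures at 12 months is half the discordance divided by P(fail). It runs from 0.0505/0.202 = 25% (SD 30, ρ = 0.9) to 0.0555/0.106, about 53% (SD 20, ρ = 0.7).

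**Timeline (incidental).** Assume enrolment starts at ethics approval. An 18-month execution with a 12-month last visit leaves 18 − 12 = 6 months to enrol 200 patients (200/6, about 33 per month). With a 6-month last visit it leaves 18 − 6 = 12 months (200/12, about 17 per month). With 24 months and a 12-month last visit it also leaves 12 months. The 18-month figure sits more easily with 6-month follow-up, but it does not settle which is meant.

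**The case against.** The strongest reply has four parts.

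First, the Section 5 sentence refers to EGG diagnosis, water volume and symptoms, so it sets no time for weight loss or success. That is correct. The 6-versus-12-month conflict rests on Section 1.3 against Sections 3.1 and 4.2, not on that sentence.

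Second, a 6-month failure criterion and a 12-month success outcome could coexist, and the first appears in the introduction. But it is adopted expressly for this protocol and no other success rule is given, so the ambiguity remains.

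Third, the objective's wording allows baseline EGG or the 3-month change to suffice, and a separate analysis plan could supply detail. Baseline and 3 months do keep the objective answerable, and this limits the weight of the point. The difficulty is not silence, however. Sections 4.7 and 5 give explicit lists that exclude a named predictor, so any later plan would have to contradict either them or Section 3.1.

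Fourth, the protocol uses its abbreviation for bariatric endoscopy loosely, and Section 4.2 appears to apply it to all four groups. The count of 100 of 200 therefore follows the wording and is not stated outright. The summary and Section 1.2 do define the term as endoscopy, and the rule cites a scale adapted to endoscopic treatment, so the narrow reading is fair. No section plans different outcome times for endoscopic and surgical patients; the text merely permits it.

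The study calls itself a pilot and its regression is exploratory. That lowers the stakes but does not remove the need to say when the primary outcome is judged.

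**Conclusion.** The concern holds and should be fixed; it is not fatal. The contradiction is read directly from the current text and needs no assumption: three visit sets, a primary predictor missing from both analysis lists, and two candidate times for the primary outcome.

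The estimate that 6.5% to 17.5% of endoscopic sleeve patients change class does rest on assumptions: the SD, the correlation and the 12-month mean. It takes the lower end of the stated 6-month mean. A higher mean at both times would reduce the number who fail and the number who change class. It describes one of four groups. Its use is to show that, with few failures, the choice of time can replace a sizeable share of the events on which a predictor is tested. The enrolment figures show tension with an 18-month timeline, not that the study is infeasible.

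**What to change.** 1. Put one assessment grid in the protocol and make Sections 3.1, 4.1, 4.3, 4.7, 5 and the timeline agree with it.
2. Name one time for clinical success, state the success or failure definition at that time for all four procedure groups, and report the other time as secondary. Twelve months matches Sections 3.1 and 4.2 as worded. If 6 months is intended, reword Section 3.1.
3. Either add the 1-month EGG to Sections 4.7 and 5 or remove it from Section 3.1.
4. If the 12-month outcome is kept, add it to Section 5 and state a duration, within the range in Section 4.2, that lets the last patient reach that visit.

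The cost is mostly wording, because Sections 4.1 and 4.3 already plan the visits. The 18-month timeline may have to lengthen, and keeping the 1-month EGG gives the blinded reader more recordings to analyse. The change should be made before any outcome is classified.
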